#### 4.3.12.3 Clinical Laboratory, Blood Samples

#### 4.3.12.3.1 Definitions and Derivations

Laboratory tests are grouped according to chemistry and haematology. Laboratory parameters are assessed at baseline as well as throughout the study.

For chemistry and haematology parameters, laboratory abnormalities with toxicity grades according to the NCI CTCAE version 5.0 are derived.

Change from baseline in haematology and clinical chemistry endpoints is calculated for each post-dose visit. CTC grades are calculated at each visit. Maximum post-baseline CTC are also calculated. Absolute values are compared to the local laboratory reference range and classified as low (below range), normal (within range or on limits of range) and high (above range). All values classified as high or low are flagged on the listings.

#### **Liver Function Parameters**

Subjects with elevated post-baseline alanine aminotransferase (ALT), aspartate aminotransferase (AST) or Total Bilirubin that fall into these categories are identified.

Liver Function Parameters	Category
ALT	• $\geq 3 \times - \leq 5 \times \text{ULN}$
AST	• $\geq 3 \times - \leq 5 \times \text{ULN}$
Total bilirubin	• $>3 \times -\leq 5 \times ULN$
ALT or AST	• $\geq 3 \times - \leq 5 \times \text{ULN}$
Potential Hy's law	• (AST $\ge$ 3 × ULN or ALT $\ge$ 3 × ULN) and (Total Bilirubin $\ge$ 2×ULN) a

**Table 7 Liver Function Parameters** 

ULN: upper limit of normal range.

a It includes all subjects who have ALT or AST $\geq$ 3xULN and total bilirubin (BILI)  $\geq$ 2xULN, and in which the elevation in transaminases precede or coincide with (that is, on the same day as) the elevation in BILI.

#### 4.3.12.3.2 Presentation

The change in each laboratory parameter from baseline to each post-baseline visit are summarised graphically.

Laboratory abnormalities occurring from the start of IP administration to the last assessment on study are presented. Worst toxicity grade, rates of grade 3-4 toxicity, and grade shifts of 2 or more from baseline to the maximum grade are presented. Summaries indicating hyper- and hypo- directionality of change are produced, where appropriate. Laboratory parameters that cannot be graded via NCI CTCAE are summarised with frequencies of post-baseline laboratory values categorized as low (L), normal (N), or high (H) using laboratory normal ranges comparing to baseline. Listings are provided for all laboratory results.

#### **Liver Function Parameters**

Number and percentage of subjects with elevated post-baseline ALT, AST or Total Bilirubin (BILI) are tabulated. Individual subject data with elevated ALT or AST plus BILI falling into the "Potential Hy's law" are summarised and listed.

#### 4.3.12.4 Clinical Laboratory, Urinalysis

#### 4.3.12.4.1 Definitions and Derivations

Change from baseline in urinalysis endpoints are calculated for each post-dose visit. CTC grades are calculated at each visit. Maximum post-baseline CTC is also calculated. Absolute values are compared to the local laboratory reference range and classified as low (below range), normal (within range or on limits of range) and high (above range). All values classified as high or low are flagged in the listings.

#### 4.3.12.4.2 Presentation

Listings are provided for urinalysis. Urinalysis endpoints are summarised by study visit which will include descriptive statistics for the value of the parameters and the changes from baseline. Absolute values and change from baseline at each timepoint are presented. Maximum post-baseline CTC grades which are not normal will be summarized.

For urinalysis, shift from baseline to worst on treatment results are presented.

Listings are provided for urinalysis.

#### 4.3.12.5 Vital Signs

#### 4.3.12.5.1 Definitions and Derivations

Vital signs (weight, body temperature, systolic and diastolic blood pressure, respiratory rate and heart [pulse] rate) are performed at timepoints as specified in the schedule of assessments. Any changes in vital signs should be recorded as an AE if applicable.

#### 4.3.12.5.2 Presentation

Vital signs are summarised by study visit which includes descriptive statistics for the value of the parameters and the changes from baseline. Absolute values and change from baseline for vital signs data at each timepoint are presented using box plots.

#### 4.3.12.6 Electrocardiogram

#### 4.3.12.6.1 Definitions and Derivations

Electrocardiogram (ECG) parameters are assessed in triplicate at baseline and subsequent triplicate measurements and should only be taken if clinically indicated. Single ECG readings are collected at visits other than baseline. ECG parameters include: PR, RR, QRS, QT, and QTcF. The QTcF is considered as the primary correction method to assess subject cardiac safety.

From these resting 12-lead ECGs values of the QT and RR intervals and the QT interval corrected for heart rate using Fridericia's correction (QTcF) is derived using the following formula:

•  $QTcF = QT/RR^{(1/3)}$  where RR is in seconds

The values of QTcF (milliseconds) are re-derived from the values of RR and QT during the creation of the reporting database.

#### 4.3.12.6.2 Presentation

ECG parameters are listed.

# 4.3.12.7 Echocardiogram/Multigated Acquisition

#### 4.3.12.7.1 Definitions and Derivations

An echocardiogram or Multigated Acquisition (MUGA) scan to assess left ventricular ejection fraction (LVEF) will be performed at the visits screening and treatment discontinuation and as clinically indicated.

# 4.3.12.7.2 Presentation

LVEF will be listed.

# 4.3.12.8 Bleeding events

Information obtained by the bleeding event questionnaires is depicted in a listing.

# 4.4 Exploratory Analyses

CCI		
CCI		
CCI	:	
• CCI		
CCI		
CCI		
CCI		

•	CCI			
-	CCI			

- CCI ,
- CCI

CCI	

•	CCI	

UI				

- CCI
- CCI

•	I

CCI		

CCI			
CCI			
CCI			
CCI			
CCI			

•

CCI	
CCI	
CCI	
4.4.2 CCI	
CCI	
CCI	
CCI	

#### 4.4.3 Biomarkers

Predictive biomarkers of ceralasertib including CCI

will be measured from samples collected for testing at Screening (Days -21 to -1) [baseline assessment] and on-treatment, Cycle 0 (on Day 7) of ceralasertib monotherapy [on-treatment assessment]. All analysis of this data will be performed on the PD Analysis Set.

**CCI** results related analyses are beyond the scope of this SAP but may be analysed at a later timepoint according to the below descriptions which might be extended to explore biomarkers even further.

results are summarised descriptively at baseline and on-treatment assessments, including change from baseline. The summary statistics provided include number of observations (n), geometric mean (calculated as  $exp[\mu]$ , where  $\mu$  is the mean of the data on a logarithmic scale), coefficient of variation (CV, calculated as  $100 \sqrt{exp(s_2)-1}$ ], where s is the standard deviation of the data on a log scale), arithmetic mean, arithmetic SD, median, minimum and maximum.

Boxplots of change from baseline will be produced on a log scale for on-treatment timepoint. The geometric means are presented using a diamond symbol in these plots.

Plots will be produced showing each patient's baseline and on-treatment results over time on a log scale with separate lines indicating the results for each patient.

Analysis of additional biomarkers, if required, will be carried out by AZ Biomarker team and covered in a separate document.

# 4.5 Pharmacokinetics

Plasma concentrations-time data are not analysed to determine the PK parameters. Pre-dose and post-dose plasma concentrations for each scheduled time-point are summarised by treatment, PK Day and Cycle using appropriate descriptive statistics. PK concentration data are listed for each subject in the safety analysis set.

Individual concentrations may be excluded from summary tables, graphical or statistical analysis for legitimate scientific reasons. Any exclusions, together with justification for the exclusion, is clearly documented in the CSR. These individual data are still presented in the listings, but are flagged to identify that they are excluded from summary outputs.

The following descriptive statistics are presented for plasma concentrations:

- n
- n below lower limit of quantification (LLOQ)
- geometric mean (gmean)
- geometric standard deviation (gSD)
- gmean±gSD
- geometric coefficient of variance (%) (gCV)
- arithmetic mean of non log-transformed data (mean)
- standard deviation of non log-transformed data (Std Dev)
- coefficient of variance (%) (CV)
- median
- minimum (min)
- maximum (max)

The gmean is calculated as  $exp(\mu)$ , where  $\mu$  is the mean of the data on the natural log scale.

The gSD is calculated as  $exp(\sigma)$ , where  $\sigma$  is the standard deviation of the data on the natural log scale.

The gCV is calculated as 100 x sqrt[ $exp(s^2)-1$ ], where s is the Std Dev of the data on the natural log scale.

The gmean  $\pm$  gSD (gmean-gSD and gmean+gSD) is calculated as exp[ $\mu \pm$ s].

Protocol scheduled times are used to present the PK concentration summary tables and corresponding gmean concentration-time figures.

Boxplots of plasma concentration at pre-dose and 1h post dose is presented for cycles until cycle 3 for both Ceralasertib and Durvalumab separately. The geometric means are presented using a diamond symbol in these plots.

# Handling of Non-Quantifiable Concentrations

Individual concentrations below the LLOQ of the bioanalytical assay are reported as NQ in the listings with the LLOQ defined in the footnotes of the relevant TFLs. Individual plasma concentrations that are Not Reportable are reported as NR and those that are missing are reported as NS (No Sample) in the listings. Plasma concentrations that are NQ, NR or NS are handled as follows for the provision of descriptive statistics:

- Any values reported as NR or NS are excluded from the summary tables and corresponding figures.
- At a time point where less than or equal to 50% of the concentration values are NQ, all NQ values are set to the LLOQ, and all descriptive statistics are calculated accordingly.
- At a time point where more than 50% (but not all) of the values are NQ, the gmean, gmean ± gSD and gCV% are set to NC. The maximum value is reported from the individual data, and the minimum and median are set to NQ.
- If all concentrations are NQ at a time point, no descriptive statistics are calculated for that time point. The gmean, minimum, median and maximum are reported as NQ and the gCV% and gmean ± gSD as NC.
- The number of values below LLOQ (n < LLOQ) are reported for each time point together with the total number of collected values (n).
- If data are available for less than three subjects, no summary statistics other than minimum, maximum and n are presented.

#### Graphical presentation of PK data

• Box plots of pre-dose and post-dose concentration mean (arithmetic mean and/or gmean) by PK visit are displayed on the same plot. Preferably, cycles are differentiated by colours on the same figure.

#### Precision and Rounding Rules for Pharmacokinetic Data /PK concentration data

PK concentration data listings are presented to the same number of significant figures as the data received from the bioanalytical laboratory (usually but not always to 3 significant figures) and against the same units as received.

PK concentration descriptive statistics present 4 significant figures with the exception of the min and max which present 3 significant figures and n and n<LLOQ which present as integers.

# 4.6 Immunogenicity

Immunogenicity results are listed for each subject and summarised for the Safety analysis set. Number and percentage of subjects in the following categories are provided.

- Anti-drug antibody (ADA) positive at baseline and/or post-baseline visits.
- Persistent positive, defined as positive at ≥2 post-baseline assessments (with ≥16 weeks between first and last positive) or positive at last post-baseline assessment.
- Transient positive, defined as negative at last post-baseline assessment and positive at only one post-baseline assessment or at ≥2 post-baseline assessments (with <16 weeks between first and last positive).
- Treatment-boosted, defined as baseline positive ADA titre that was boosted to a 4-fold or higher level following drug administration.

All valid assay results from subjects who receive any study drug are included in immunogenicity summaries. Blood samples collected outside of the protocolled window are summarised at the closest nominal time point that does not already have a value. All subjects with titre information are shown in the data listing.

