## **3.2** General Considerations

The below-mentioned general principles will be followed throughout the study:

- Summary tables are produced by treatment group. Total columns are produced for non-efficacy tables.
- Descriptive statistics will be used for all variables, as appropriate.
  - Continuous variables will be summarised by the number of observations, mean, standard deviation, median, upper, and lower quartiles where indicated, minimum and maximum. For log-transformed data (ie, pharmacokinetic [PK] concentration data) it is more appropriate to present geometric mean, coefficient of variation (CV), median, minimum, and maximum.
  - If data are available for less than 3 subjects, no summary statistics other than minimum, maximum and number of observations are presented.
  - Categorical variables will be summarised by frequency counts and percentages for each category. Unless otherwise stated, percentages will be calculated based on the analysis set population total, by treatment group and by timepoint as appropriate.
- For continuous data, the mean, standard deviation and median are rounded to one additional decimal place compared to the original data. Minimum and maximum are displayed with the same accuracy as the original data.
- Time-to-event variables will be presented using the Kaplan-Meier (KM) methodology, including median time calculated from the KM curves.
- For categorical data, percentages are rounded to one decimal place with the exception of 100% which is presented as a whole number.
- SAS® version 9.4 (or higher) and/or other validated software (as appropriate) will be used for the analyses. In case R is used, the R build version and the version of each used R package will be documented.

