## **Table 5 Analysis Sets**

Analysis set	Description	Endpoint/Output
Enrolled analysis set	All subjects who sign the informed consent form (ICF).	Disposition
Safety analysis set	All subjects receiving at least 1 dose of study treatment. Subjects are summarised according to the actual treatment received.	Exposure Safety ORR BOR TTR DoR EORTC IL PGI-TT PK concentration listings Percentage Change in Target Lesion Tumour size Best Percentage Change in Target Lesion Tumour size
BICR Modified safety analysis set	All subjects receiving at least 1 dose of study treatment who have measurable disease at baseline	ORR (interim) BOR (interim) DCR (interim)

Analysis set	Description	Endpoint/Output
	by BICR and who have first dose at least 9 weeks prior to data cut off.	
Investigator Modified safety analysis set	All subjects receiving at least 1 dose of study treatment who have measurable disease at baseline by Investigator and who have first dose at least 9 weeks prior to data cut off.	ORR (interim) BOR (interim) DCR (interim)
Full analysis set	All subjects who are randomised in the study. The FAS is used for all the efficacy analyses including PROs. Treatment arms are summarized on the basis of randomised study treatment, regardless of the treatment actually received. Subjects who were randomised but did not subsequently receive study treatment are included in the analysis in the treatment arm to which they were randomised.	Baseline and demography ORR (for comparative analysis) PFS OS PROs
Pharmacokinetics (PK) analysis set	All dosed subjects with reportable ceralasertib or durvalumab plasma concentrations. Subjects are summarised according to the treatment received.*	PK concentrations
Pharmacodynamic analysis set	All subjects who receive at least 1 dose of study treatment with at least 1 reportable post-baseline pharmacodynamic measurement. Subjects are summarised according to the treatment received.*	Pharmacodynamic endpoints
BICR Response evaluable set	All dosed subjects who have measurable disease at baseline by BICR	ORR (sensitivity analysis)
Investigator Response evaluable set	All dosed subjects who have measurable disease at baseline by Investigator	ORR (sensitivity analysis)
BICR Interim response evaluable	All dosed subjects who have measurable disease at baseline by BICR assessment and who have first dose at least 17 weeks prior to data cut off.	ORR (interim) BOR (interim) DCR (interim)

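### Persistent, transient and treatment-boosted ADA percentages are taken on all dosed subjects, including those without the samples needed to be classified

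*SAP*

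**What the plan says.** Main SAP, Section 4.6: "Immunogenicity results are listed for each subject and summarised for the Safety analysis set". Numbers and percentages of subjects are planned for four categories. The first is "Anti-drug antibody (ADA) positive at baseline and/or post-baseline visits". The other three are persistent positive and transient positive, both defined on post-baseline assessments, and treatment-boosted, defined as a rise from a positive baseline titre. The section adds: "All valid assay results from subjects who receive any study drug are included in immunogenicity summaries".

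Main SAP, Table 5 defines the Safety analysis set as "All subjects receiving at least 1 dose of study treatment". It asks for neither an ADA sample nor a durvalumab dose. The table has no ADA-evaluable set.

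Main SAP, Section 3.2 gives the default rules: "Summary tables are produced by treatment group"; "Total columns are produced for non-efficacy tables"; and "Unless otherwise stated, percentages will be calculated based on the analysis set population total, by treatment group and by timepoint as appropriate".

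The sub-study SAP repeats the Section 4.6 wording and has the same Safety set definition in its Table 6. Its Section 3.2 also bases percentages on the analysis set, but it has no Total-column rule, and every subject there is planned to receive durvalumab from Cycle 1.

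**The concern.** A subject can be persistent or transient positive only if post-baseline samples were taken and gave valid results. Treatment-boosted also needs a baseline titre. A dosed subject who lacks these cannot enter the numerator but is counted in the denominator, so a missing result is reported as if it were not positive.

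Such subjects are foreseeable. In the main study a combination-arm subject joins the Safety set with ceralasertib on Day 1, while durvalumab is given on Day 8. In the sub-study ceralasertib starts in Cycle 0 and durvalumab comes on Day 8 of Cycle 1. Both SAPs plan a disposition row for subjects who did not receive durvalumab. Early progression or withdrawal can also leave a subject with no post-baseline sample.

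What is at stake is a descriptive safety table whose post-baseline rows fall as early dropout rises, whatever the immunogenicity of the drug. In the main SAP the Total column adds a second dilution, because it pools an arm that is not planned to receive durvalumab.

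**Working it through.** The SAP states no ADA rate, number sampled or power for ADA, so there is no figure to reproduce. The check is to settle which denominator the text prescribes and then do the arithmetic.

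**Which denominator**

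1. Section 4.6 names the Safety analysis set for the summary.
2. Table 5 makes that set everyone dosed.
3. Section 3.2 applies the analysis set total unless something else is stated, and Section 4.6 states no other denominator.
4. The by-timepoint qualifier in Section 3.2 does not change this, because the ADA categories classify a subject across visits.
5. Table 5 treats comparable data differently. The PK set requires reportable concentrations, and the pharmacodynamic set requires at least one reportable post-baseline measurement.

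**Inputs**

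- Arm sizes: about 100 combination and 50 monotherapy subjects (main SAP, Section 3.2.2).
- p, the rate among evaluable combination subjects: not given; assumed 8%, with 3% and 10% as a range.
- e, the share of the combination arm with the needed samples: not given; assumed 0.70 to 1.00.
- Monotherapy arm: assumed to have no positives, which supposes that the ADA is against durvalumab.

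**Combination column** = p × e

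| e | p = 3% | p = 8% | p = 10% |
|---|---|---|---|
| 1.00 | 3.0% | 8.0% | 10.0% |
| 0.90 | 2.7% | 7.2% | 9.0% |
| 0.80 | 2.4% | 6.4% | 8.0% |
| 0.70 | 2.1% | 5.6% | 7.0% |

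The relative understatement is 1 − e, that is 0% to 30% over this range.

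**Total column, main SAP only** = p × e × 100/150

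- p = 8%, e = 1.00: 8/150 = 5.3%.
- p = 10%: 6.7% at e = 1.00 and 4.7% at e = 0.70.
- p = 3%: 2.0% at e = 1.00 and 1.4% at e = 0.70.

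The Total column thus shows 0.67 (e = 1.00) down to 0.47 (e = 0.70) of the evaluable combination-arm rate.

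**First category.** A subject with only a baseline sample can be positive here, so the dilution argument does not carry over in the same form. The separate weakness is that the row counts positives present before treatment together with those that arise afterwards, so it is a prevalence. None of the four rows isolates treatment-emergent ADA.

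**The case against.** The strongest counter-argument is that Section 4.6 never names a denominator, and that its sentence on valid assay results could be read as basing the summary on subjects who have such results. That would displace the Section 3.2 default. The sentence does not go that far: it says which results enter the summary, not who is counted in the percentage. At best it leaves room for two readings, which is itself a reason to fix the denominator.

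Two stronger readings are tempting, and the text does not support them.

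- A reader might infer that the monotherapy arm lowers the combination-arm percentages. It does not. Tables and percentages are by treatment group, so that arm has its own column and enters only the Total, which stands beside the arm-level figures. In the sub-study the question does not arise.
- A reader might infer that ADA incidence is understated. Section 4.6 has no incidence row; only the three rows that depend on post-baseline data are affected in the way shown.

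Other points stand. The target of the ADA, whether the monotherapy arm is sampled, and the sampling schedule are not in the SAP and may properly be left to the protocol. If nearly everyone has a post-baseline sample, the within-arm bias is close to zero. The table is descriptive, with no test or decision rule, and counts and individual listings are provided. The illustrated shift of 0.8 to 2.4 points is small beside sampling error: 8/100 has an exact 95% interval of about 3.5% to 15.2%. These limit the consequence, but they are no reason to count an unsampled subject as not positive.

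**Conclusion.** The point holds for the persistent, transient and treatment-boosted rows in both SAPs. As written, their percentages are understated within an arm by the share of dosed subjects who lack the samples needed. That share cannot be derived from the SAP. Over an assumed 0% to 30% unsampled, the relative understatement is 0% to 30%; 8% becomes 7.2%, 6.4% or 5.6% at 10%, 20% or 30%. These figures take the rate among evaluable subjects as the quantity of interest.

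The Total column of the main SAP carries a further factor of 100/150, provided that the ADA is against durvalumab and the monotherapy arm has no positives. The effect is confined to that column.

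No primary or secondary efficacy result is touched. The change is still worth making, because the bias has a known direction and comes from the stated rule.

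**What to change.** In Section 4.6 of both SAPs, replace the Safety set as denominator for the ADA percentages with category-specific evaluable denominators among durvalumab-treated subjects:

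- persistent and transient positive: at least one valid post-baseline ADA result;
- treatment-boosted: valid baseline and post-baseline results.

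Show the evaluable n for each row. Do not require baseline plus post-baseline results for every row: that would drop subjects with a missing baseline whose post-baseline results already allow them to be classed as persistent or transient.

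Confirm in the text which drug the ADA assay concerns. In the main SAP, omit the Total column for the ADA table. Keep the Safety set for the listings.

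Add a treatment-emergent row (baseline negative and post-baseline positive, plus treatment-boosted), reported apart from baseline positivity and based on subjects with valid baseline and post-baseline results.

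The cost is a set definition and a table-shell edit in each SAP, with somewhat smaller denominators. No new data are needed.
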